Next, the results of the study would be submitted for presentation at a regional or National conference pertinent to primary care providers, rheumatology and preventive cardiology audience. Options include American College of Physicians, Quality improvement conferences, American College of Rheumatology, American Heart Association and Women's health Conferences. Preparation and publication of the manuscript will be the pivotal step in disseminating the outcomes. Potential target journals for submission could be from Internal Medicine, Preventive Medicine, Cardiovascular, Outcomes or Rheumatology based. General Medicine Journals targeted could include Journal of American Medical Association, Lancet,

while cardiology journal circulation may be of interest. Rheumatology journals of interest would include *Journal of Rheumatology, Arthritis Care and Research, Annals of Rheumatic Diseases* or *Arthritis Research & Therapy.* Publication of data may encourage discussion or statement from the National organizations with strategies to increase CVD risk awareness and screening. Continuing medical education activities could be built based on the results dissemination.

We feel that web-based EI could reach many more RA patients in a timely fashion without using many resources. In addition, this strategy could provide patients ease, flexibility and privacy with their educational module administration. National organizations such as the Arthritis Foundation and with support of such web-based resources through unrestricted educational funds could further mobilize this intervention to across the globe.

K. Project Timeline: Major study processes and data accrual with corresponding anticipated timeline are shown below in figure 1. Deliverables and timelines for entire project are shown in Table 5 below.

Table 5: Project Timeline and Deliverables			
Deliverable	Tasks	Date	
Institutional Review Board	Regulatory documents, HIPPA etc for RUMC and JSH	1/1/2015-3/1/2015	
Develop Study Documents	Defining processes, training of research assistant, study cordinator, incentives/parking organization	1/30/2015-3/1/2015	
CVR Surveys	Modify the existent survey tools, Obtain permission for use of surveys, Collaborative meetings to discuss content and format, Develop Case Scenarios for Physicians, Reviews, Refinement, Pretest surveys	3/1/2015 to 5/30/2015	
You tube Educational module-Pat	Focus group, gather pertinent content, parse information, develop transcripts, assess understandibility level, schedule recording, recording, editing, pretesting, refining	6/30/2015	
You tube Educational module-Phy	Gather pertinent content, parse information, develop transcript, assess reading/understandibility level, schedule recording, recording, editing, pretesting, refining	6/30/2015	
RA and PHCP recruitment status	At RUMC and JSH	7/1/2015 to 7/1/2016	
Medical Chart reviews for RA patients Baseline	Identification of PHCP, review of records, data entry	7/1/2015 to 7/30/2016	
Identification of PHCP, review of	Identification of PHCP, review of records,	7/1/2016 to 8/15/2017	
records, data entry-One year Follow up	data entry		
Data Management	Data entry, data cleaning, simple analysis	7/15/2015 to 10/15/2017	
Simple Results	Statistical analysis, interpretation	11/15/2017	
Presentation of Results	Abstracts writing, submission and presentation	11/15/2017 to 1/1/2018	
Manuscript	Writing of manuscript, submission	12/30/2017 to 3/31/2018	

L. Additional Information: Abbreviations glossary is provided below.

RA (Rheumatoid Arthritis); PHCP (Primary health care provider); EI (Educational intervention); CVD (Cardio-vascular disease); CVR (Cardiovascular risk); CAD (Coronary artery disease); CVRA (Cardiovascular risk awareness); CVRS (Cardiovascular risk screening);RUMC (Rush University Medical Center), JSH (John H Stroger Hospital); PI (Primary investigator); Co-I (Co investigator); NIH (National Institute of Health).

M. References:

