We propose a longitudinal of 300 RA (150 with and 150 without EI), to test for (*primary outcome*) change in CVRA at 2-3 months following web-based EI, and compare that with CVRA changes among RA patients without IE. The proposed secondary outcomes will explore the rates of CVRS via medical chart review among RA patients with and without IE. Consenting participants (RA patients (n=300) and PCHPs) will have (a) baseline survey on CVRA, followed by a short EI delivered via YouTube video (n=150), followed by immediate and 2-3-month follow up surveys, to quantitate changes in CVRA, (b) a medical record review of participating RA patients (n=300) will be undertaken (records from preceding one year duration) and at 12 months (after baseline visit) to determine the changes in CVRA evaluations and the EI. Care will be taken to avoid enrollment of PCHPs providing care to RA patients not in the EI arm, to not confound the results.

Educational approach is discussed in the section I. We expect to reach out to 600 RA patients at RUMC and JSH, with the goal of recruiting 300 RA patients over 12 months. This screening-to-enrolment ratio is consistent with previously observed 10:9 ratio for survey-based one-visit

studies at RUPC and JSH. We expect to reach our expected goal of 300 RA patients even if screening-to-enrollment ratio erodes to 10:5. Sample size calculation: To show an improvement of 20% in overall CVRA, with 90% power and 0.05% alpha error, we need 127 RA patients in each group.

H. Innovation: We did not find on our review of current medical literature (PubMed and Ovid Medline) using the search terms "Rheumatoid arthritis" and "educational intervention" and "web" for any existent EI studies that study patient-PHCP CVRA or utilize a YouTube based EI to improve CVRA. Furthermore, use of patient-PHCP dyad for CVR EI has not been reported. We feel confident that our study idea is original and has significant advantages over existent methods as it is easier, quicker and has significant potential applications. The you tube video EI if successful can be offered through National organizations e.g. American College of Rheumatology or Arthritis Foundation; and can be made available to large numbers of RA patients worldwide with less resources utilization and advantages of privacy, flexibility and access to users.

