Exploratory Analysis: Patient and PHCP correlates of CVRS and changes in CVRS in RA; Change in PHCPs CVRA	CVRS and changes in CVRS, Change in CVRA for PHCPs	Modifiable patient and PHCP correlates of CVRS and changes in CVRS would be identified. PHCP CVRA is modifiable.	Predictors of CVRS or change in CVRS will allow evidence based development of targeted strategies for patient and PHCP to improve CVRS in RA for future. Improvement in CVRA in PHCP will help facilitate further studies, interventions, and PQRI incentives	

CVRA: Eighteen modifiable and non-modifiable traditional CVR being assessed are (a) Fifteen Non-modifiable and modifiable CVR: Age, Male gender, Postmenopausal status, Ethnicity, Family history of premature CVD (in father at age <55 yrs, or mother at age <65 years), smoking, dyslipidemia, hypertension, physical inactivity, obesity (>20% over ideal body weight), diabetes, stress, excessive alcohol, autoimmune diseases (e.g. RA), steroids, and (b) three RAspecific (Disease activity, duration, use of steroids).

CVRS: Checklist used to assess CVRS will include only primary CVR factors, and these will include elicitation of history of diabetes (if present, glycosylated hemoglobin annually in diabetics), dyslipidemia (if present, lipid panel in past one year), hypertension (if present, control of blood pressure in past one year), rheumatoid arthritis (Steroids, lipid panel in past one year), smoking (if present, education for cessation in past one year), poor activity level (if present, education on exercise in past one year), obesity (if present, BMI and/or weight loss education documentation in past one year), family history of CVD.

Data Collection: All consecutive patients with a diagnosis of RA seen in the Rheumatology clinics will be sought for participation. Inclusion criteria: A. *RA patients*: Adult men and women

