meeting the following criteria (i) Diagnosed with RA with following criteria: Inflammatory symmetric polyarthritis of \geq 6 weeks, with physician documented synovitis in medical records (past or current) consistent with RA, with or without rheumatoid factor, anti cyclic citrullinated peptide or radiologic evidence of RA. Exclusion of another etiology for above. (ii) Receipt of care by rheumatologist at either RUMC or JSH. This will allow us access to full medical records to correctly gauge the prevalence of CVRS. (iii) Informed consent. *B. PHCP*: (i) Physicians providing primary care to the RA patients recruited for this study for the El group. Definition of PHCP has been previously provided (section F), (ii) Informed consent (iii) Not providing PHCP to RA patients in the non-El group.

1.2. *Methods: 1.* Education intervention development phase: The primary outcome of the intervention development phase will be patient-centered EI video and PHCP-centered education EI to increase CVRA in RA. The interdisciplinary study team will develop a multi-level web-based EI for CVRA targeted to RA patients and their PHCPs. This team will consist of 3-6 RA patients and the panel of experts in rheumatology, preventive cardiology/endocrinology, and experimental health and social psychology. To improve overall RA patient outcomes, our educational approach for the web-based EI is specifically aimed at changing the knowledge, and thus health behaviors of RA patients and their PHCP.

Educational Approach: In the **development of the web-based EI** (Table 1, Figure 1), we will utilize credible, useful, innovative educational platform and input from opinion leaders in the therapeutic areas. All educational content will be learner centric in approach, language and content (Table 2). Content appropriateness of the tailored intervention will be verified by the health experts. Processes of change will be focused on increasing RA patients or their PHCP CVRA in general and in RA, and increasing their awareness of the need for change. This 20-30 minute You Tube EI video will be developed using scientifically researched content (Table 2).

	Table 2: Develo	opment of Content for Educational web-based Intervention
Audience	Major Areas in Content Develo	Key Features
Patients	1) What is CVD and CVD in USA	Definition of CVD, Leading cause of death
	2) CVD in Women	Leading cause of death in women

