Participant	Procedure	Baseline (Day 0)	FU 1 (Day 0)	FU 2 (2-3 month)	FU (1 Year)
Focus Group (RA) n=5	Informed Consent	٧			
	Demographics	V			
	Interviews	٧			
	CVR Survey	V.	1253		
	Honorarium (\$25)	V	Region		
Pretest (RA) n=10	Informed Consent	V	and the second s		
	Demographics	V	- The		
	You Tube Video	V	10	(a)	
1.4	Interviews	V			
4	CVR Survey	V		2	
14	Honorarium (\$25)	V		30	
RA patients n=150 (EI)	Informed Consent	V		第	
1. Sec. 1.	Demographics	V		14 C	
E.	CVR Survey	V (in person)	√ (In person)	v (In person)	
80	You Tube Video	V		22	
1	Honorarium (\$25)	٧		V	
23	Medical Chart	٧	1 N	2	V
RA Patients n=150 (non El)	Informe d Co nsent	Drove	ed /	1	
22	Demographics	V	11	13	
24	CVR Survey	√ (In person)	1	V (In person)	
14	You Tube Video		1	5	
	Honorarium (\$25)	٧	14	V	
	Medical Chart Review	V	AT THE A		٧
РНСР	Informed Consent	V	- Tele		
n=50	Demographics	V	[name]		
	CVR Survey	√ (Email)	V (Email)		
	You Tube Video	V	-		

I. Pilot-testing phase procedures are summarized in Table 4 and figure 1.

Assessment of CVRA in Patients: After informed consent, each participant will be assigned a unique study number, which will be used to pair data from the pre- and post-intervention visits. Participants will be given an online survey to fill to assess their CVRA (*Baseline Patient survey*). A You Tube video will be shown to the patient on a tablet or a computer screen. The video recording will be of 20-30 minutes duration to avoid attention fatigue. Immediately after viewing the video, each patient will be given the CVRA online survey (*Follow up Patient survey* 1). An exit online credibility survey will be used to gather feedback on credibility (user-friendliness, content, understandability, and relevance), barriers experienced in using the webbased intervention and any suggestions (open-ended). To assess retention of knowledge, between 2-3 months after the baseline visit the second post-intervention assessment (*Follow up Patient survey* 2) using the same CVRA survey will be administered online. Follow up survey

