2 will be paired data. Medical charts records will be reviewed to quantify prevalence of CVRS by PHCP (within one-year period preceding baseline visit) at baseline and one-year follow up visit. For patients whose PHCP is not within Rush University Medical Center or John H Stroger Hospital, we will contact their local PHCP to obtain their pertinent medical records to quantify prevalence of CVRS by PHCP (within one-year period preceding baseline visit) at baseline and one-year follow up visit. Study participants will be asked to provide informed consent to communicate with their PHCP and access to their medical records to allow for assessment of CVRS.

Assessment of CVRA in PHCPs: PHCPs will be contacted by email. Acceptance to proceed with the study online will be taken as informed consent. Online survey on their CVRA (*Baseline PHCP survey*) will be evaluated using case scenarios developed specifically for this purpose, followed by a You-Tube video developed using evidence based literature review, specially including autoimmune diseases and risk of CVD in women and RA. This will be developed at the level of the targeted audience and of 20-30 minutes duration. They will then be prompted to take the same case scenario based survey immediately to assess their CVRA (*Follow up PHCP survey 1*). An exit online credibility survey will be used to gather feedback on credibility (user-friendliness, content, understandability, and relevance), barriers experienced in using the webbased intervention and any suggestions (open-ended).

I.3.Tools:

IRB

Survey to assess CVRA: The survey will include the following components:

1. The content of Patient surveys: Brief survey to collect demographic and self reported past medical history, family history, Social history and current medications, current weight and height. This will be administered to RA.

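### The baseline screening (CVRS) year is fixed by the patient's visit alone, so where a PHCP has several EI patients a later patient's baseline can include months after the PHCP saw the video, which may dilute the Aim 2B change

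*Protocol*

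**What the plan says.** **Windows.** Section I.2 (Assessment of CVRA in Patients) has the charts reviewed to "quantify prevalence of CVRS by PHCP (within one-year period preceding baseline visit) at baseline and one-year follow up visit". Section G.1 says the same in other words: "records from preceding one year duration" for baseline, and a second review "at 12 months (after baseline visit"). Items in the CVRS checklist in section I.1 carry a matching look-back, for example "lipid panel in past one year". All of these dates come from the patient.

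**PHCP exposure.** A PHCP becomes eligible through patients already in the study: "Physicians providing primary care to the RA patients recruited for this study" for the EI group. PHCPs are contacted by email, complete a survey, watch their video and repeat the survey (section I.2, Table 4). No interval between a patient's enrolment and the PHCP's viewing is given.

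**Timing and numbers.** Table 5 has a single line, "RA and PHCP recruitment status", running from 7/1/2015 to 7/1/2016. Table 4 lists "RA patients n=150 (EI") and 50 PHCPs.

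**Safeguard.** A PHCP must meet the condition "Not providing PHCP to RA patients in the" non-EI group, and section G.1 promises care on the same point. Nothing deals with later EI patients of a PHCP who has already watched.

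**Use.** Table 1 expects CVRS in EI patients to be higher at one year than at baseline. Section I.7 compares the change in CVRS between EI and non-EI by chi-square.

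**The concern.** A before/after measure of provider behaviour needs a baseline that precedes the provider's exposure. Here that holds for the first EI patient of each PHCP but not necessarily for the next. Suppose a PHCP watches the video on 7/1/2015 because of one patient, and a second of that PHCP's patients enrols on 4/1/2016. The second patient's baseline year runs from 4/1/2015 to 4/1/2016, and 9 of its 12 months follow the video. The plan counts all 12 as pre-intervention.

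If the PHCP video increases screening, as the project intends, EI baseline CVRS is raised and the baseline-to-one-year change in the EI group is understated. The between-group comparison of change loses the same amount, provided non-EI baselines are unaffected. A small or null Aim 2B result could then not be told apart from a diluted one, because the plan does not record the date needed to separate them. The patient's own video plays no part, since it is shown after the baseline window closes.

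**Working it through.** The plan gives no figure for this overlap. Its one sample-size statement (127 per group) concerns CVRA and does not enter here. The steps below give a range under stated assumptions.

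**Inputs from the Protocol**
- Recruitment period 12 months (Table 5); baseline look-back 12 months (G.1, I.2).
- 150 EI patients and 50 PHCPs (Table 4). 150/50 = 3 per PHCP only if every EI patient's PHCP takes part.

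**Assumptions**
- Patients enrol uniformly over the 12 months.
- The PHCP watches L months after the first of his or her n EI patients enrols.

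**Overlap with no lag (L = 0).** The expected enrolment time of the i-th of n patients is 12i/(n+1). The i-th patient therefore has 12(i−1)/(n+1) post-video months in the baseline year, and the mean over n patients is 6(n−1)/(n+1).

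| EI patients per PHCP | Mean post-video months in baseline year | Share of 12 |
|---|---|---|
| 1 | 0 | 0% |
| 2 | 6×1/3 = 2.0 | 17% |
| 3 | 6×2/4 = 3.0 (0, 3 and 6 by order) | 25% |
| 5 | 6×4/6 = 4.0 | 33% |
| 10 | 6×9/11 = 4.9 | 41% |

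**Overlap with a lag, n = 3.** With x = L/12, the second patient's expected overlap is 3(1−x)⁴ months and the third's is 12(0.5 − x + x³ − x⁴/2).
- L = 1: 2.12 and 5.01, so the mean is (0 + 2.12 + 5.01)/3 = 2.4 months (20%).
- L = 3: 0.95 and 3.16, so the mean is (0 + 0.95 + 3.16)/3 = 1.37 months (11%).

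Simulation gives the same values. The share of EI patients with any overlap is 67%, 58% and 42% for L = 0, 1 and 3.

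**Effect on the CVRS change.** Take a true rise from 45% to 65%. The 45% is the lipid-screening rate for older RA patients cited in section E; the 20 points are assumed, since the Protocol's 20% refers to CVRA. With n = 3 and L = 0:
- If exposure acts in proportion to time, baseline becomes 45 + 0.25×20 = 50%, and the measured change is 65 − 50 = 15 points.
- If screening occurs at a constant rate before and a higher constant rate after the video, simulation gives a baseline of 50.5% and a measured change of 65 − 50.5 = 14.5 points, so 5.5/20 = 28% of the rise is hidden.

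With n = 1 and L = 0 nothing is lost.

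**The case against.** The strongest objection is that the size is not in the documents, and this stands. Three patients per PHCP is a quotient of two planned totals, not a stated cluster size. PHCPs must consent, are approached by email and may practise outside the two hospitals. Fifty participating PHCPs could each have a single EI patient, with no overlap.

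The rule excluding PHCPs of non-EI patients may also shrink clusters. The allocation method is not stated. If it were individual and 1:1, a PHCP with three study patients would have all three in EI with probability 1/8. If all 300 patients came in pairs from 150 PHCPs, 150/4 = 37.5 PHCPs would be EI-only, covering 75 of the 150 EI patients, and mean overlap across the arm would be 0.5 × 2/12 = 8%. On the other side, section F lets a rheumatologist be the PHCP and section B counts 15 salaried rheumatologists, so some clusters could be large.

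Four stronger readings are tempting and are not supported:
- **A known loss of a quarter of the effect.** The 25% is one scenario. Table 5 gives a shared period for patients and PHCPs, not an order.
- **A guaranteed one-sided bias between groups.** The plan intends to keep exposed PHCPs out of the non-EI arm but does not ensure it. The direction also depends on the video raising screening.
- **A matching fault in follow-up.** A PHCP who watches late leaves unexposed months in the patient's follow-up year. That is the intervention as delivered, not an error.
- **A predictable distortion of the planned correlation between PHCP CVRA and baseline CVRS.** For later patients that baseline may be partly post-video, but no direction has been derived.

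It can also be said that a sensitivity analysis belongs in an SAP. That is fair for its details. But the Protocol itself fixes the window, and no later analysis can recover a viewing date that was not collected.

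**Conclusion.** The point holds as a design weakness in a secondary, exploratory outcome. Both CVRS windows are tied to the patient's visit, EI PHCPs are exposed on their own date within the same 12 months, and nothing stops a later EI patient's baseline year from including post-video practice. If the video works, the EI change in Aim 2B is diluted.

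The size is undetermined. It is zero with one EI patient per PHCP, or if each PHCP is emailed only after all of his or her EI patients have enrolled. It is 3 of 12 months (25%) with three per PHCP, uniform accrual and no lag, and about 1.4 months (11%) with a 3-month lag. Any loss in percentage points also rests on an assumed true effect. The primary CVRA comparison is unaffected, and the bias would hide an effect rather than create one. It merits correction because the remedy is cheap and the missing date may not be recoverable afterwards.

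**What to change.** 1. In section I.2, and in the PHCP data list in section I.6, add the date on which each PHCP first viewed the video. The fidelity paragraph says only that the web system tracks how long a participant stayed on the video, so the date should not be presumed available.
2. Keep the visit-anchored baseline year as planned for the main Aim 2B comparison.
3. Add a stated Aim 2B analysis for EI patients whose PHCP viewed before their own Day 0. Either end their baseline year at the PHCP's viewing date or exclude them, and name the choice in advance. Non-EI windows stay as they are.
4. Report CVRS change in EI patients by whether the PHCP viewed before or after the patient's Day 0.

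**Cost.** One extra date field, and a chart look-back reaching up to 12 months earlier for some EI patients. Re-anchoring has two drawbacks to state openly. Those EI baselines shift by up to 12 months in calendar time relative to non-EI baselines, so a secular trend in screening could enter the comparison. The months between the PHCP's viewing and the patient's Day 0 also fall in neither window. Exclusion avoids both but loses patients: under three per PHCP and no lag it would keep about 150 × (1 − 0.67) ≈ 50 EI patients, and with a 3-month lag about 150 × (1 − 0.42) = 87. For these reasons the analysis supplements the planned window and does not replace it.

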A. Title: Web (YouTube) based educational intervention to improve patient-physician awareness of cardiovascular risk in rheumatoid arthritis

B. Organizational detail: Rush is a not-for-profit health care, education and research enterprise. Rush University Medical Center (RUMC) encompasses a 664-bed hospital. The mission of RUMC is to provide the best care for our patients. A unique combination of research and patient care has earned Rush national rankings in 9/ 16 specialty areas in *U.S. News & World Report*'s 2013-14 America's Best Hospitals issue. Our education and research endeavors, community service programs are dedicated to enhancing excellence in patient care in the Chicago area. RUMC's core values — innovation, collaboration, accountability, respect and excellence —translate into highest quality patient care. The Department of Medicine's leadership is dedicated to supporting research endeavors to improve patient care. Hence, *both the organization and departmental leadership are committed to improving patient care and research*.

The Division of Rheumatology at RUMC (and its affiliated institutions) provides care to patients with rheumatoid arthritis (RA), and thus has access to large numbers of RA patients to pursue research. The division includes 15 salaried MD rheumatologists at two clinical locations. At RUMC, we see approximately 500 RA patients per year. John Stroger Hospital (JSH) is affiliated and in vicinity of RUMC. The primary investigator (PI) has clinical privileges at both the hospitals. The JSH's Rheumatology division provides longitudinal care for rheumatology patients, mostly with poor or no medical insurance. Approximately 1000 RA patients per year are seen by Rheumatology at JSH. Our combined (RUMC and JSH) Rheumatology division's leadership and faculty are actively engaged in investigator-initiated clinical trials, including quality improvement projects.

The Department of Preventive Medicine at RUMC has been specializing in design and testing of rigorous multi-level interventions for cardiovascular risk reduction. The proposed study will have access to its statistical and methodological expertise, including experts in cardiovascular prevention, cardio-metabolic conditions and behavioral science. The resources of the Department of Preventive Medicine will enhance the methodological rigor and likelihood of success of this study.

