Perception of risk of heart disease scale (PRHDS) (8), Heart Disease Fact Questionnaire (HDFQ)(24) will be modified to include some items on autoimmune diseases (including RA).Relevant components of the Behavioral Risk Factor Surveillance System (BRFSS) 2013 survey from US Centers for Disease Control 2013 (22), This will include sections and modules on hypertension awareness (2 items), cholesterol awareness (3 items), chronic health conditions (12 items), tobacco use (5 items), pre diabetes and diabetes (10 items), cardiovascular health (7 items), Mental Illness and Stigma (10 items) and Emotional Support and life satisfaction (2 items).

2. The content of PHCP surveys: A survey to assess CVRA in PHCPs will be developed. This survey development will be guided by the co-investigators and a questionnaire adapted from BRFSS and National Health and Nutrition Examination Survey (21) that was used previously in a similar study (8). The survey will be modified to include questions about CVRA in women and in autoimmune diseases. In addition, five hypothetical case scenarios will be created with various combinations of CVR in patients with and without autoimmune disease, and PHCP will be asked to select the CVRS indicated and strategies to optimize the patient's individual CVD risks.

The finalized surveys used for CVRA will be pretested among 5-10 RA patients and Physicians.

I.4. Incentives: For the participating RA, a \$50 honorarium will be provided at baseline and follow up visit (Table 4).

I.6. Data: *Patient*: Demographic (age, gender, ethnicity), Socio-economic status (education) and RA pertinent data (duration, presence of Rheumatoid factor and/or anti cyclic citrullinated peptide, bony erosions, medications (including steroids and biologics)). Self reported CVRA (Overall, Traditional and RA) will be assessed at baseline, immediately after viewing the video (follow up 1), and after 2-3 months (follow up 2).

PHCP: Demographic (age, gender, ethnicity), type of physicians (Internal Medicine, Family practice, Rheumatologist), years since completion of residency in Internal Medicine or Family Practice, years since board certification, currently board certification status, setting of practice (academic, community or private practice), rank (if any), approximate number of RA patients seen yearly. Self reported CVRA (Overall, Traditional and RA) will be assessed at baseline, immediately after viewing the video (follow up 1), and after 2-3 months (follow up 2).

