For patients (a) Overall CVRA (ORA), (b) Traditional CVR awareness (TRA) (c) RA CVR awareness (RARA) will be calculated. Awareness of all 18 CVR being tested (listed in section 1) will denote 100% CVR awareness. To score ORA, patient's correct responses denoting awareness to each of the 18 CVR being tested will be calculated in percentage of total responses. Domain-specific CVR awareness for traditional CVR (TRA) and RA (RARA) will be scored separately using the same strategy.

CALL AND AND A

Paired t tests to compare pre and post (Follow up 2) patient overall CVRA for our primary outcome of interest will be performed. Effect size of gains in overall CVRA for RA patients after EI (Follow up survey 2 and baseline) will be calculated. We will then compare percent change in overall CVRA rates (between baseline and follow up 2) using chi square analysis, among EI and non-EI patients with RA. A p value of ≤ 0.05 will be considered significant on two tailed tests.

Aim 2B. To explore changes in cardiovascular risk screening (CVRS) at the primary health care visits among RA patients with and without EL.

The medical records of RA patients with and without EI will be reviewed in electronic medical record, and analyzed using standardized checklist to assess the prevalence of CVRS and CVD risk reduction plan (meaningful use). Changes in CVRS rates among EI and non EI groups will be calculated, and compared using chi square analysis. A p-value of ≤ 0.05 will be considered significant on two tailed tests.

Exploratory analysis on improvement in PHCP overall CVRA using analysis similar to those discussed for aim 2a will be undertaken, a post hoc power analysis and effect size will be obtained. In addition exploratory univariate and multivariate logistic or linear regression analysis for patient and PHCP correlates of CVRS (baseline) and change in CVRS will be performed. Improvements in Traditional and RA-specific CVRA among RA and PHCPs will be assessed.

J. Dissemination plan: The first step in disseminating outcomes will be to share the results of the study with the participants of the study, RA patients and their PHCP.

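### Insurance and recruiting site are not listed as patient data or covariates, so an imbalance in coverage would go unseen in the unadjusted screening comparison and could colour the exploratory correlates of screening

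*Protocol*

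**What the plan says.** Protocol I.6 lists the patient variables as "Demographic (age, gender, ethnicity), Socio-economic status (education) and RA pertinent data", the last being duration, serology, erosions and medications. I.3 adds a "Brief survey to collect demographic and self reported past medical history, family history, Social history and current medications, current weight and height" and selected BRFSS content: "This will include sections and modules on hypertension awareness (2 items), cholesterol awareness (3 items), chronic health conditions (12 items"), followed by tobacco, diabetes, cardiovascular health, mental illness and emotional support. None of these eight sections is about coverage or access to care. The CVRS checklist in I.1 does not name insurance either.

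Section B says of the two sites: "The JSH's Rheumatology division provides longitudinal care for rheumatology patients, mostly with poor or no medical insurance". It adds: "Approximately 1000 RA patients per year are seen by Rheumatology at JSH", against about 500 at RUMC.

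For the analysis, I.7 compares changes in CVRS rates between EI and non-EI patients by chi-square. It also states that "exploratory univariate and multivariate logistic or linear regression analysis for patient and PHCP correlates of CVRS (baseline) and change in CVRS will be performed". Table 1 gives the purpose of that regression: "Modifiable patient and PHCP correlates of CVRS and changes in CVRS would be identified", as a basis for targeted strategies.

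**The concern.** CVRS counts care received over a year: lipid panels, glycosylated hemoglobin, blood pressure control, counselling. Coverage plausibly affects whether a patient gets these, and the protocol itself presents coverage as a feature of its larger site. Two analyses are exposed.

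- **Aim 2B, EI versus non-EI.** G.1 proposes 150 patients with and 150 without the video and does not describe how patients enter each group. Providers enrolled for the EI group must not also be primary providers of non-EI patients, which ties group to provider and could also tie it to clinic and coverage. The I.7 baseline comparison covers demographics and disease characteristics only, and the outcome test has no covariates.
- **Correlates of CVRS.** Ethnicity and education are the social predictors listed in I.6. If they are related to coverage, their coefficients on baseline CVRS may partly reflect access. Strategies built on them could then be aimed at the wrong factor.

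**Working it through.** The protocol gives no figure for CVRS by group, site or insurance, so there is no planned figure to reproduce. The G.1 sample size (127 per group) concerns awareness (CVRA) and is not touched by this point.

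**1. Is coverage or site recorded anywhere?** Four places were compared: the I.6 patient list, the I.3 brief survey, the I.3 BRFSS sections and the I.1 checklist. Insurance is named in none. Site follows from eligibility (rheumatology care at RUMC or JSH), so it is known for every patient, but it is not listed as a variable or covariate.

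**2. How much of the recruitment pool is concerned?** From section B: 1000 / (1000 + 500) = 66.7% at JSH and 33.3% at RUMC.

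**3. Would allocation balance it?** Suppose allocation were random and recruitment followed volume (an assumption). The chance difference between groups in RUMC share would then have standard deviation sqrt(0.333 × 0.667 × 2/150) = 0.054, or 5.4 percentage points, and the test would keep its nominal level. No random allocation is described, so this protection cannot be assumed. Nor do the documents say that the groups differ by site.

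**4. What does an imbalance do to Aim 2B?** Let D be the difference between groups in the share of patients with good coverage. Let b1, b0 be baseline screening rates with good and poor coverage, and f1, f0 the one-year rates, with no video effect.

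- Difference between groups in *level* at one year: D × (f1 − f0).
- Difference between groups in *change*: D × [(f1 − b1) − (f0 − b0)].

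I.7 compares change. If coverage shifts the screening rate equally at both times, then f1 − b1 = f0 − b0 and the second expression is zero. A false difference needs both an imbalance (D not zero) and a coverage effect on the trend. Where the video works, a coverage effect on patients' ability to act on it would also alter the estimated effect.

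**5. What does it do to the correlates regression?** Baseline CVRS is a level, so nothing cancels. If two ethnic or education groups differ in coverage by D, an omitted coverage effect of (b1 − b0) adds D × (b1 − b0) to the crude difference between them. The documents give neither D nor b1 − b0.

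**6. Can section E supply the missing number?** It cites lipid screening of 26% for patients seeing a rheumatologist alone and 44–48% with some primary care visits. The cited study's title in the reference list says its patients were on Medicare, so they had coverage. The contrast is between patterns of care, not between insured and uninsured, and cannot be used for b1 − b0.

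**The case against.** Several objections have force.

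- **I.6 is not a closed list.** I.3 collects medical, family and social history, weight and height, which the I.6 patient line omits. A reader might infer from I.6 that coverage can never be known, but the documents do not support that. Charts are reviewed for all 300 patients at baseline and one year, and coverage may be retrievable. Still, nothing says it will be abstracted, and consent to records access is described as serving CVRS assessment, so it is better named in advance.
- **Site is already a proxy.** It is coarse, since JSH patients are only mostly poorly covered, but it could be used. A reader might infer that access cannot be separated from the video at all; that is too strong.
- **Aim 2B compares change.** As step 4 shows, a stable coverage difference largely cancels. This stands and narrows the concern.
- **The deeper defect in the group comparison is the undescribed allocation together with the unadjusted test.** This also stands. Recording insurance helps only if the analysis uses it.
- **The regression is exploratory and looks for modifiable correlates.** This is true and lowers the stakes, especially for ethnicity. It does not remove the possible misreading of the coefficients.

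**Conclusion.** The point holds in limited form. Education is the only socio-economic item listed, and neither insurance nor site is a stated data item or covariate, although the site with about two thirds of the RA volume is described as serving mostly poorly insured or uninsured patients. With no random allocation described and an unadjusted chi-square, an imbalance in site or coverage between the groups would be neither displayed nor corrected. In the regression of baseline CVRS, ethnicity and education coefficients may partly reflect access.

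A reader might be tempted to put a size on the bias by treating the section E lipid-screening gap as an insurance effect. The documents do not support that, for the reason in step 6, and no magnitude should be stated.

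Severity is minor to moderate: Aim 2B is secondary, the regression is exploratory, and the awareness outcome is not at issue. The conclusion rests on two assumptions: that coverage influences receipt of screening, and that it may differ between the EI and non-EI groups or across ethnic and education groups. The protocol makes both plausible but quantifies neither.

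**What to change.** 1. Add insurance type and recruiting site to the I.6 patient data, taken from the records already being reviewed.
2. Report both by EI and non-EI group in the baseline table.
3. Include both as covariates in the CVRS-correlates regression.
4. Supplement or replace the Aim 2B chi-square with a comparison adjusted for baseline CVRS, site and baseline insurance.

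The cost is one or two extra abstracted fields per patient and a few model degrees of freedom. No visits or patients are added, and the sample size does not change. Adjustment reduces confounding by these two factors; it does not replace a description of how patients are allocated.
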